3.3.2 Rationale for Patient Population

The safety and efficacy of RO7496998 (AT-527) in hospitalized adult patients with moderate COVID-19 who have risk factors for poor outcome is currently being investigated in a Phase II study (AT-03A-001). Given the significant unmet need and disease burden in those with mild to moderate disease in the outpatient setting, this Phase III study is designed to further evaluate the efficacy and safety of RO7496998 (AT-527) in this population. Using the FDA guidance for industry (FDA 2020a), mild and moderate COVID-19 baseline severity categorization is defined as follows:

- Mild COVID-19
 - Positive testing by standard reverse-transcriptase polymerase chain reaction (RT-PCR) assay or equivalent test
 - Symptoms of mild illness with COVID-19 that could include fever, cough, sore throat, malaise, headache, muscle pain, gastrointestinal symptoms, without shortness of breath or dyspnea
 - No clinical signs indicative of Moderate, Severe, or Critical Severity
- Moderate COVID-19
 - Positive testing by standard RT-PCR assay or equivalent testing
 - Symptoms of moderate illness with COVID-19, which could include any symptom of mild illness or shortness of breath with exertion
 - Clinical signs suggestive of moderate illness with COVID-19, such as respiratory rate ≥ 20 breaths per minute, $\text{SpO}_2 > 93\%$ on room air at sea level, heart rate ≥ 90 beats per minute
 - No clinical signs indicative of Severe or Critical Illness Severity

In this study, *otherwise* healthy adult and adolescent patients without risk factors, as well as adult and adolescent patients with risk factors for hospitalization, will be enrolled. Randomization will be stratified based on the presence of one or more risk factors for severe COVID-19 as well as geographic region. Although the inclusion of a risk factor increases the individual risk of hospitalization, the course and progression of disease in those with mild to moderate disease alone should be similar irrespective of the presence or absence of a risk factor or the specific underlying risk factor.

The true incidence of SARS-CoV-2 infection in the pediatric population is currently unknown, and it is unclear whether adolescents are as susceptible to infection by SARS-CoV-2 compared with adults. Recent evidence suggests that those aged < 18 years are likely to have the same or higher viral loads in their nasopharynx compared with adults and that adolescents can spread the virus effectively in households (Heald-Sargent et al. 2020; Park et al. 2020). Whilst children and adolescents infected with SARS-CoV-2 are less likely to develop severe illness compared with adults, they are still at risk for developing severe illness and complications from COVID-19 especially if they have underlying risk factors.

Adolescents in this study will need to meet the symptom severity criteria as per adults, therefore, the benefit of RO7496998 (AT-527) is still likely to be seen in this population. *Approximately* 100 adolescents will be recruited to the study, with a maximum of 150 adolescents. Similar PK characteristics are expected for adolescents compared with adults and also in those who are healthy compared to those at high risk for poor disease outcome. It is also expected that efficacy and virological endpoints will show consistent results in adolescents compared with adults.

Although more severe COVID-19 illness can occur in individuals of all ages, it primarily occurs in older adults or those with underlying medical conditions, including cardiovascular disease, diabetes mellitus, hypertension, chronic lung disease, obesity (body mass index [BMI] > 30), cancer, and chronic kidney disease (CDC 2020b; Lighter et al. 2020; Wu and McGoogan 2020; Zhou et al. 2020).

The following are considered high-risk factors for hospitalization for adults and will be used for the purposes of stratification:

- Age \geq 65 years
- Obesity, defined as BMI > 30
- Cardiovascular disease, including hypertension
- Chronic lung disease, including moderate to severe asthma
- Chronic metabolic disease, including diabetes
- Chronic kidney disease
- Chronic liver disease

- Immunocompromised (e.g., active cancer, HIV or AIDS, use of corticosteroids and immunosuppressants)

The following are considered high-risk factors for hospitalization for adolescents and will be used for the purposes of stratification:

- BMI \geq 85th percentile for their age and gender based on CDC growth chart

Boys: <https://www.cdc.gov/growthcharts/data/set1clinical/cj41l023.pdf>
 Girls: <https://www.cdc.gov/growthcharts/data/set1clinical/cj41l024.pdf>
- Sickle cell disease
- Congenital or acquired heart disease
- Neurodevelopmental disorders (e.g., cerebral palsy)
- Asthma, reactive airway disease, chronic respiratory disease that requires daily medication for control
- Diabetes
- Immunosuppressive disease

3.3.3 Rationale for Control Group

A placebo-controlled study design for the evaluation of RO7496998 (AT-527) will allow unbiased evaluation of both safety and efficacy of RO7496998 (AT-527). There is a lack of targeted treatments for COVID-19 and none currently approved for those with mild-moderate disease and not requiring hospitalization. Supportive or symptomatic treatment is the mainstay of treatment for this patient population. Participants in this study will be allowed to use appropriate rescue treatment as detailed in Section 4.3.3. Therefore, a placebo-control arm is appropriate in this study.

3.3.4 Rationale for Biomarker Assessments

COVID-19 is a heterogeneous disease, and expression of certain biomarkers has been shown to vary among patients, especially those that are hospitalized (Arunachalam et al. 2020). Therefore, all patients may not be equally likely to benefit from treatment with RO7496998 (AT-527). Predictive biomarker samples collected prior to dosing will be assessed in an effort to identify those patients with COVID-19-driven pathogenesis who are most likely to respond to RO7496998 (AT-527). PD biomarkers will also be assessed to demonstrate evidence of anti-viral activity of RO7496998 (AT-527) and the resulting changes in the host immune response in patients. Given that these biomarkers may also have prognostic value, their potential association with disease progression will also be explored.

3.3.5 Rationale for Non-Standard Clinical Outcome Assessments

At the onset of the global emergency, there was limited understanding of what constituted disease progression in COVID-19 and how the symptoms experienced by patients manifested themselves and affected their lives. Given the heterogeneous nature of COVID-19 related symptoms in outpatients, key COVID-19 related symptoms

should be assessed systematically to provide an accurate evaluation. Symptom alleviation has also been used as a registrational endpoint for influenza therapies. The precedent for the use of patient-reported symptoms in influenza provides key insights on how to apply a similar strategy to COVID-19, especially given that approximately 80% of patients with COVID-19 are treated in the outpatient setting and symptom alleviation is an important marker of clinical benefit for these patients. Furthermore, FDA guidance (FDA 2020b), notes resolution of symptoms as an example of important clinical outcomes. For this reason, the example FDA COVID-19 patient-reported outcome (PRO) instrument has been used as a basis for the COVID-19 Symptom Diary assessing 14 key symptoms and will be used for this study. The symptom items used in this PRO are derived from information provided by the Centers for Disease Control and Prevention as of 28 August 2020. *Optional exit interviews will be conducted in a subset of patients (up to 80 patients in limited countries) to support content validity of the COVID-19 Symptom Diary.*

4. MATERIALS AND METHODS

4.1 PATIENTS

Approximately 1386 non-hospitalized patients (including approximately 100 adolescents, up to a maximum of 150, with the remaining patients being adults) with mild to moderate COVID-19, with or without high-risk factors will be enrolled in this study.

4.1.1 Inclusion Criteria

Patients must meet the following criteria for study entry:

- Written informed consent/assent for study participation obtained from patient, parent, or patient's legal guardian, with assent as appropriate by the patient, depending on the patient's level of understanding
- Age ≥ 18 years (regardless of weight) at the time of signing informed consent or age ≥ 12 to < 18 years (weight ≥ 40 kg) at the time of signing informed consent (and assent)
- Ability to comply with all aspects of the study protocol, including providing samples for virology, in the opinion of the investigator
- At least three of the following symptoms of at least moderate (score ≥ 2 as per COVID-19 Symptom Diary) intensity: nasal congestion or runny nose, sore throat, cough, shortness of breath, muscle or body aches, fatigue, headache, chills or sweats, feeling hot or feverish, nausea, vomiting, or diarrhea.
- Positive SARS-CoV-2 diagnostic test (RT-PCR or validated rapid antigen test) ≤ 72 hours prior to randomization

A historical record of positive result (RT-PCR and validated rapid antigen test) from test conducted ≤ 72 hours prior to randomization is acceptable. Note: sites should record the details of a patient's screening test in the eCRF. Home tests are not acceptable and would require a site confirmatory test.

- Symptoms consistent with mild or moderate COVID-19, as determined by the Investigator, with onset \leq 5 days before randomization
- For women of childbearing potential and girls at or beyond menarche (age \geq 12 to $<$ 18 years): agreement to remain abstinent (refrain from heterosexual intercourse) or use adequate contraception during the treatment period and for 30 days after the final dose of RO7496998 (AT-527).

A woman is considered to be of childbearing potential if she is postmenarchal, has not reached a postmenopausal state (\geq 12 continuous months of amenorrhea with no identified cause other than menopause), and is not permanently infertile due to surgery (i.e., removal of ovaries, fallopian tubes, and/or uterus) or another cause as determined by the investigator (e.g., Müllerian agenesis). The definition of childbearing potential may be adapted for alignment with local guidelines or regulations. Women of childbearing potential must be established on their chosen method of contraception at screening.

The following are examples of adequate contraceptive methods: bilateral tubal ligation; male sterilization; hormonal contraceptives; hormone-releasing intrauterine devices; copper intrauterine devices; male or female condom with or without spermicide; and cap, diaphragm, or sponge with spermicide.

Hormonal contraceptive methods must be supplemented by a barrier method.

The reliability of sexual abstinence should be evaluated in relation to the duration of the clinical trial and the preferred and usual lifestyle of the patient. Periodic abstinence (e.g., calendar, ovulation, symptothermal, or postovulation methods) and withdrawal are not adequate methods of contraception.

If required per local guidelines or regulations, locally recognized adequate methods of contraception and information about the reliability of abstinence will be described in the local Informed Consent Form.

4.1.2 Exclusion Criteria

Patients who meet any of the following criteria will be excluded from study entry:

- Clinical signs indicative of COVID-19 illness requiring hospitalization defined as any of the following:
 - In adults: respiratory rate \geq 30, heart rate \geq 125 bpm, SpO₂ \leq 93% on room air
 - In adolescents: respiratory rate \geq 30, heart rate \geq 130 bpm, SpO₂ \leq 93% on room air
- Admitted to a hospital prior to randomization or is hospitalized (inpatient) at randomization due to COVID-19

Note: If local policy requires COVID-19 isolation or internment in a hospital or similar facility, such as in Japan, but those patients otherwise meet the inclusion criteria, this exclusion may not apply.

- In the opinion of the investigator, is likely to experience imminent deterioration and require hospitalization
- Treatment with an investigational drug within 5 half-lives or 3 months (whichever is longer) of randomization
- Treatment with a COVID-19 therapeutic agent including, but not limited to, other direct or indirect acting antivirals *against SARS-CoV-2 (such as remdesivir or favipiravir), systemic or inhaled steroids (such as dexamethasone or inhaled budesonide), colchicine, ivermectin, interferons, convalescent plasma, monoclonal antibodies against SARS CoV-2 or interleukin 6 (IL-6), intravenous immunoglobulin or other EUA-approved treatments within 3 months or less than 5 drug elimination half-lives (whichever is longer) prior to the screening visit*
- Concomitant use of P-glycoprotein (P-gp) inhibitors or inducers listed in Section 4.4.3
- Known allergy or hypersensitivity to components of study drug
- Pregnant or breastfeeding, or intending to become pregnant during the study or within 30 days after the final dose of RO7496998 (AT-527)

Women of childbearing potential must have a negative pregnancy test result at screening prior to initiation of study drug.

- Abnormal laboratory test results at screening, defined as meeting any of the following sets of criteria:
 - ALT or AST $>5 \times$ upper limit of normal (ULN)
 - Total bilirubin $>1.5 \times$ ULN, unless the patient has known Gilbert disease
 - Creatinine clearance $<60 \text{ mL/min}$
 - Total WBC $<2,500/\text{mm}^3$ or ANC $<800/\text{mm}^3$
 - Platelet count $<80/\text{mm}^3$

Local laboratory test results from standard-of-care tests performed prior to obtaining written informed consent and ≤ 48 hours before randomization may be used; such tests do not need to be repeated for screening

- Requirement of any prohibited medications during the study
- *Other known active viral or bacterial infection at the time of screening, such as influenza*

Note: This exclusion does not apply to patients with stable chronic viral infections, such as chronic HCV or HIV providing other eligibility criteria are met.

- Any clinically significant medical condition or laboratory abnormality that, in the opinion of the investigator, could jeopardize the safety of the patient or affect patient compliance or safety/efficacy observations during the study
- *COVID-19 vaccination within ≤ 40 -days prior to enrollment (second dose if applicable); see Section 4.5.2 for documentation requirements pertaining to vaccine type and date of dosing*

4.2 METHOD OF TREATMENT ASSIGNMENT AND BLINDING

4.2.1 Treatment Assignment

This is a randomized, double-blind study. After initial written informed consent has been obtained, all screening procedures and assessments have been completed, and eligibility has been established for a patient, the study site will obtain the patient's identification number and treatment assignment from an IxRS.

Patients will be randomly assigned to one of two treatment arms: RO7496998 (AT-527) or matching placebo. Randomization will occur in a 2:1 ratio of RO7496998 (AT-527) to placebo through use of a permuted-block randomization method to ensure a balanced assignment to each treatment arm. Randomization will be stratified by region and high-risk factor for hospitalization due to COVID-19 for (see Sections 3.1 and 3.3.2 for details).

4.2.2 Blinding

Study site personnel and patients will be blinded to treatment assignment during the study. The Sponsor and its agents will also be blinded to treatment assignment, with the exception of individuals who require access to patient treatment assignments to fulfill their job roles during a clinical trial. These roles include the unblinding group responsible, clinical supply chain managers, sample handling staff, operational assay group personnel, IxRS service provider, and iDMC members.

While PK samples must be collected from patients assigned to the comparator arm to maintain the blinding of treatment assignment, PK results for these patients are generally not needed for the safe conduct or proper interpretation of the study data. Laboratories responsible for performing study drug PK will be unblinded to patient treatment assignments to identify appropriate samples for analysis. PK samples from patients assigned to the comparator arm will not be analyzed for study drug PK concentration except by request (e.g., to evaluate a possible error in dosing).

If unblinding is necessary for a medical emergency (e.g., in the case of a serious adverse event for which patient management might be affected by knowledge of treatment assignment), the investigator will be able to break the treatment code by contacting the IxRS. The treatment code should not be broken except in emergency situations. The investigator is not required to contact the Medical Monitor prior to breaking the treatment code. However, the investigator should contact the Medical Monitor to discuss emergency unblinding after the treatment code has been broken.

As per health authority reporting requirements, the Sponsor's Drug Safety representative will break the treatment code for all serious, unexpected suspected adverse reactions (see Section 5.7) that are considered by the investigator or Sponsor to be related to an investigational medicinal product (IMP; defined in Section 4.3). The patient may continue to receive treatment, and the investigator, patient, and Sponsor personnel, with

the exception of the Drug Safety representative and personnel who must have access to patient treatment assignments to fulfill their roles (as defined above), will remain blinded to treatment assignment.

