- Proportion of patients with any post-treatment infection
- Proportion of patients with all-cause mortality

Duration and time to event secondary efficacy endpoints will be analyzed using similar methods as specified for the primary endpoint. Patients who are lost to follow-up, who do not have a response, or who die will be censored at their last contact date or date of death, whichever is applicable. Kaplan-Meier plots, median time to response, 95% CIs, and p-values will be presented.

Frequency and proportion secondary efficacy endpoints will be analyzed using a Cochran-Mantel-Haenszel test adjusted by the stratification factors at baseline, region (North America, Europe, ROW) and high-risk factor (yes, no), unless stated otherwise. The proportions and difference in proportions, together with a 95% CI and p-values will be presented.

COVID-19 related complications (i.e., radiologically confirmed pneumonia, acute respiratory failure, sepsis, coagulopathy, pericarditis/myocarditis, and cardiac failure) will be adjudicated per blinded manual medical review of events, together with other related eCRF data (e.g., Adverse Event forms as applicable and medical history) by an internal adjudication team before the study readout. Further details will be provided in an internal adjudication charter.

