If an interim analysis is conducted for virology, the Sponsor will be unblinded. The interim analysis will be conducted by the Sponsor to confirm adequate antiviral effect. Patients that contribute to the virology interim analysis will be excluded from the final efficacy and virology analyses, and will be replaced in order to maintain power of the primary endpoint analysis and there will therefore be no alpha adjustment for the final analysis. The interim virology analysis will involve an early look at virology parameters over time and may include formal statistical analysis of the change from baseline in viral titer. Details will be specified in a separate interim SAP which will be finalized prior to the interim analysis taking place.

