1.2.1 Treatment Assignment and Blinding

Patients will be randomly assigned to one of two treatment arms: RO7496998 (AT-527) or matching placebo. Randomization will occur in a 2:1 ratio of RO7496998 (AT-527) to placebo through use of a permuted-block randomization method to ensure a balanced assignment to each treatment arm. Randomization will be stratified by region (North America, Europe, and rest of the world [ROW]) and presence of a high-risk factor (yes, no) for hospitalization due to COVID-19 (see Protocol Sections 3.1 and 3.3.2 for details). A minimum of 40% of the overall study sample will have a high-risk factor for hospitalization because of COVID-19. A minimum of 40% will also be expected for the otherwise healthy population. Stratification caps will be implemented within interactive voice/Web-based response system (IxRS) to ensure these requirements are met.

Study site personnel and patients will be blinded to treatment assignment during the study. The Sponsor and its agents will also be blinded to treatment assignment, with the exception of individuals who require access to patient treatment assignments to fulfill their job roles during a clinical trial (see Protocol Sections 4.2.2 for details).

If unblinding is necessary for a medical emergency (e.g., in the case of a serious adverse event [SAE] for which patient management might be affected by knowledge of

treatment assignment), the investigator will be able to break the treatment code by contacting the IxRS.

As per health authority reporting requirements, the Sponsor's Drug Safety representative will break the treatment code for all serious, unexpected suspected adverse reactions (see Protocol Section 5.7) that are considered by the investigator or Sponsor to be related to an investigational medicinal product (IMP; defined in Protocol Section 4.3).

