1.2.2 Sponsor Review and Adjudication

Sponsor representatives from clinical science who are independent of the study team will review data from the study for the purposes of adjudicating adverse events (AEs) identified by the investigator as COVID-19-related complications. This adjudication will determine medically confirmed COVID-19-related complications, which will be used for the frequency of COVID-19-related complications endpoint. These complications and the role and process of Sponsor review and adjudication will be specified in a separate charter.

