If there is a potential for the study to be stopped for futility as a result of the interim analysis, the threshold for declaring futility will include an assessment of the predictive probability that the specified endpoint will achieve statistical significance.

If an interim analysis is conducted for virology, the Sponsor will be unblinded. The interim analysis will be conducted by the Sponsor to confirm adequate antiviral effect. Patients that contribute to the virology interim analysis will be excluded from the final efficacy and virology analyses, and will be replaced in order to maintain power of the primary endpoint analysis and there will therefore be no alpha adjustment for the final analysis. The interim virology analysis will involve an early look at virology parameters over time and may include formal statistical analysis of the change from baseline in viral titer. Details will be specified in a separate iSAP, or by updating this SAP which will be finalized prior to the interim analysis taking place.

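### If the optional virology interim is run, the plan unblinds the Sponsor without limiting this to a team or to the interim patients' codes, which goes beyond the job-role exception in its own blinding section

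*Protocol*

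**What the plan says.** **Blinding.** Protocol 4.2.2 states: "The Sponsor and its agents will also be blinded to treatment assignment, with the exception of individuals who require access to patient treatment assignments" as part of their job. It then gives examples: "These roles include the unblinding group responsible, clinical supply chain managers, sample handling staff, operational assay group personnel, IxRS service provider, and iDMC members". SAP 1.2.1 carries the same rule ("The Sponsor and its agents will also be blinded to treatment assignment") and refers back to 4.2.2.

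**Virology interim.** Protocol 6.8.1 and SAP 5.8.1 plan no interim analysis. Protocol 6.8.2 and SAP 5.8.2 let the Sponsor choose one efficacy look, one virology look, or both. For virology, Protocol 6.8.2 says: "If an interim analysis is conducted for virology, the Sponsor will be unblinded. The interim analysis will be conducted by the Sponsor". SAP 5.8.2 has the same rule ("If an interim analysis is conducted for virology, the Sponsor will be unblinded"), and so does the protocol synopsis. The stated purpose is in 6.8.2: "The interim analysis will be conducted by the Sponsor to confirm adequate antiviral effect". Patients in the look leave the final efficacy and virology analyses and are replaced, and no alpha is spent. Details are left to an interim SAP or a SAP update, to be final before the look.

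**Efficacy interim.** The same sections keep the Sponsor blinded, with an external statistical group running the analysis and the iDMC reviewing it.

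**Adjudication.** Protocol 6.4.2 says that the listed COVID-19 complications "will be adjudicated per blinded manual medical review of events", by an internal team. SAP 1.2.2 says who does it: "Sponsor representatives from clinical science who are independent of the study team will review data from the study". SAP 5.4.1.3 places the complications endpoint among the key secondary endpoints.

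**The concern.** One section confines treatment codes to people who need them for their job. Another, if its option is used, hands them to the Sponsor with no qualifier. Protocol 9.5 shows that the Sponsor is two companies, both providing medical monitoring. It is also the Sponsor whose internal team is meant to review complications blind.

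What is at stake is operational bias, not type I error from a repeated test. Staff who know whether the drug is lowering viral RNA would go on monitoring and adjudicating a double-blind trial. Virology is not a side issue here: time to cessation of viral shedding by RT-qPCR is itself a key secondary endpoint (SAP 5.4.1.5). Blinding lost at an interim cannot be restored, so the wording needs settling before the option is used.

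**Working it through.** **1. Power is not the problem.** Inputs from SAP 3: hazard ratio 1.25, two-sided alpha 0.025, power 90%, 2:1 allocation. By Schoenfeld's formula,

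events = (z₀.₉₈₇₅ + z₀.₉₀)² / [p(1 − p)(ln HR)²] = (2.2414 + 1.2816)² / [(2/3)(1/3)(0.2231)²] = 12.411 / 0.011065 ≈ 1122,

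which is the plan's figure. Then 1122/0.90 = 1246.7 (plan: 1248 evaluable) and 1248/0.90 = 1386.7 (plan: about 1386 randomised). Because interim patients are replaced, the 1122-event target stands. The documents give no size for the look. If 50, 100, 200 or 300 evaluable patients (assumed) were dropped without replacement, events would be 0.9 × (1248 − m) = 1078.2, 1033.2, 943.2 or 853.2, and power 88.7%, 87.3%, 83.9% or 79.7%. Replacement avoids that loss.

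**2. Who may hold codes.** The list in 4.2.2 is introduced as examples, so it is open. A small Sponsor group assigned to the interim could fit the exception. The Sponsor as a whole could not, because most of its staff do not need codes for their work. No study-team, statistics, virology-analysis or adjudication role is on the list.

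**3. Whether the word Sponsor is only shorthand.** In Protocol 6.8.2 the efficacy look keeps the Sponsor blinded and the virology look unblinds it. The same word has opposite status in parallel sentences, and no sub-team, patient subset or firewall is named. The section offers these sentences as its integrity specifications. An interim SAP could define a team, but it would be narrowing an unqualified protocol statement.

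**4. What exclusion and replacement achieve.** They stop the same data being used twice and so support spending no alpha. They say nothing about who sees the by-arm result. They also cover only the final efficacy and virology analyses: the safety-evaluable set in SAP 4 does not drop these patients, who may still be in follow-up to Day 33 when their codes are opened.

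**5. What remains in Sponsor hands after a look.**
- Medical monitoring, shared with a contract research organisation (Protocol 9.5).
- Adjudication of complications (Protocol 6.4.2, SAP 1.2.2).
- The choice between IxRS and eCRF strata, which depends on an undefined degree of imbalance (SAP 5.1).
- The proportional-hazards check that can switch the primary test, which is graphical with no numeric rule (SAP 5.3.2). The plot is by arm and so is read after final unblinding anyway. The point there is that the rule should be settled before anyone knows an arm-level result.
- Protocol 6 has the SAP signed off before unblinding, without saying whether an interim unblinding counts.

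**6. Share of codes opened, for scale only.** With m randomised patients in the look and all replaced, the share is m/(1386 + m). For an assumed m of 100 it is 100/1486 = 6.7%; for 300 it is 300/1686 = 17.8%. This describes exposure of codes. It is not an estimate of bias.

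**The case against.** Much of the case on the other side stands.

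- The look is optional and unplanned. If it is never run, the sections do not conflict.
- Both documents require full details, including integrity specifications, to be set down beforehand. A SAP update for the interim is therefore a step before the look. A reader might infer that the Sponsor may rewrite the SAP once it knows the result; the text does not say that.
- A reader might infer that the number randomised or the pooling of strata would be steered by the result. Protocol 6.1 ties the first to the RT-qPCR-positive percentage and the event count, and SAP 5.1 ties the second to low or zero counts. Neither depends on arm-level data.
- A reader might infer that adjudicators will be unblinded. That follows only from the bare word Sponsor. The protocol calls the review blinded and the SAP places it outside the study team. Deaths and hospitalisations are taken as the investigator reports them, and SAP 5.4.1.3 adds a sensitivity analysis on investigator-reported complications.
- The primary endpoint is a diary completed by patients who, like site staff, stay blinded. The documents show no direct route from Sponsor knowledge of viral RNA to diary scores. Safety analyses are descriptive.
- If only the interim patients' codes are opened, nobody in the final efficacy analysis is unblinded.

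Two things are left. The limit in the last bullet is nowhere stated. And nothing keeps the by-arm result from the people running the trial. Independence from the study team does not shield adjudicators from an unblinding that applies to the whole Sponsor.

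**Conclusion.** The point holds, conditionally. If the virology interim is run, Protocol 6.8.2 and SAP 5.8.2 unblind the Sponsor more widely than Protocol 4.2.2 and SAP 1.2.1 allow, and they sit badly with the blinded internal review of a key secondary endpoint. Excluding and replacing the interim patients deals with data reuse and power, but not with knowledge of the by-arm antiviral result during enrolment and follow-up.

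The stronger reading, that the trial's decisions would no longer be blinded or that the primary result would be biased, is not supported: the look may not happen, several of the decisions are tied to pooled quantities, and patients and sites stay blinded. The size of any bias cannot be derived from the documents. The 6.7% to 17.8% share of codes rests wholly on an assumed look of 100 to 300 patients. This is a change worth making because it is cheap and cannot be made retrospectively.

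**What to change.** In Protocol 6.8.2, the synopsis and SAP 5.8.2, replace the sentence that unblinds the Sponsor with a rule to this effect: *a named group with no role in study conduct, medical monitoring, adjudication, SAP changes or the final analysis (internal, or an external statistical group) will have access to the treatment codes of the virology-interim patients only; the study team and adjudicators remain blinded to codes and by-arm results until database lock.* Change the sentence on who conducts the look to match.

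Add the group to the list in Protocol 4.2.2, to which SAP 1.2.1 already refers. State in Protocol 6 and SAP 5.8.2 that the main SAP is final before any interim unblinding.

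The cost is an amendment to wording. The study team would see only the decision, not the by-arm virology data. The external group is foreseen at present only for the efficacy interim, so if it is chosen for a virology-only look its contract must cover that work.
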